7.4.1.2 Timing

Adverse events will be assessed after the subject signs informed consent/assent and at all study visits.

Treatment-emergent AEs include any untoward medical occurrence in a subject or clinical investigation subject after administration of an investigational study treatment, which does not necessarily have to have a causal relationship with this treatment. A treatment-emergent AE can therefore be any unfavorable and unintended sign (including an abnormal laboratory finding), symptom, or disease temporally associated with the use of the product, whether or not related to the medicinal (investigational) product. It could also include accidents and reasons for changes in medication (drug and/or dose).

Treatment-related AEs are all treatment-emergent AEs that are considered by the investigator as causally related to administration of the study drug.

7.4.1.3 Severity of Adverse Events

The investigator is to classify the severity (intensity) of an AE according to the following definitions:

- Mild – The subject was aware of the signs and symptoms but the signs and symptoms were easily tolerated.
- Moderate – The signs and symptoms were sufficient to restrict, but did not prevent, usual daily activity for the subject.
- Severe – The subject was unable to perform usual daily activity.

The maximum intensity of an AE (mild, moderate, or severe) will be assessed taking into account the possible range of intensity of the symptom(s).

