2.5 Benefit-risk Assessment

Sirolimus (Rapamune), an immunosuppressant, is approved in the US as an orally administered agent for the prophylaxis of organ rejection. The package insert reports that the most common (> 30%) adverse reactions are peripheral edema, hypertriglyceridemia, hypertension, hypercholesterolemia, creatinine increased, abdominal pain, diarrhea, headache, fever, urinary tract infection, anemia, nausea, arthralgia, pain, and thrombocytopenia. There is also a boxed warning that increased susceptibility to infection and the possible development of lymphoma and other malignancies may result from immunosuppression.

In the current study with topical administration of sirolimus, systemic exposure to sirolimus is expected to be very low. In literature reports of topically-applied sirolimus and everolimus for the treatment of facial angiofibromas,⁸⁻¹⁸ only 1 subject had a detectable blood levels of sirolimus (0.8 mmol/L).¹⁷ Additionally, the topical treatment was well tolerated and no systemic or local adverse effects were reported.

Patients might benefit from the trial, because it is expected that the facial angiofibromas will improve. There is currently no FDA approved pharmaceutical treatment for this disease condition. The risks of participation in the trial include the risks associated with the study procedures (e.g., blood drawing) which are similar to other trials of investigative agents. No systemic or local adverse effects were reported in previous clinical experience with topical sirolimus, although these studies were small. The study has been designed and will be conducted in such a manner as to minimize risks as much as possible. Therefore, the benefit-risk assessment is considered acceptable for a first multiple-dose trial in human.

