7.4 Assessment of Safety

7.4.1 Adverse Events

7.4.1.1 Adverse Events Assessments

An adverse event (AE) is an untoward medical occurrence in any subject during the study which does not necessarily have a causal relationship with the study drug treatment. Adverse events can be categorized as treatment-emergent or treatment-related. All AEs will be recorded and will be documented in the CRFs.

AEs will be collected from the time the subject signs informed consent/assent until 30 days after the last investigational product administration. Serious adverse events (SAEs) must be reported to the sponsor within 24 hours of awareness. The condition of the subject will be monitored

throughout the study for any signs or symptoms. The occurrence of AEs should be sought by nondirective questioning of the subject at each visit during the study. All AEs will be collected as:

- The subject's positive response to questions about their health.
- Symptoms spontaneously reported by the subject.
- Clinically relevant changes and abnormalities observed by the investigator (e.g., local and systemic tolerability, laboratory measurements, results of physical examinations, monitoring for infections and noninfectious pneumonitis).

If an AE worsens in intensity, it should be recorded as a new AE. Otherwise, it continues as the first report (counted as the same AE) until the subject is recovered.

The investigator or designee will record the following on the AE CRF:

- Adverse event and relevant clinical findings
- Time/date of onset
- Time/date of recovery
- Intensity
- Action taken on study drug/treatment
- Other action taken to treat the event
- Relation to study drug/treatment
- Seriousness of the AE

Adverse events requiring therapy must be treated with recognized standards of medical care to protect the health and well-being of the subject. Treatment due to an AE will be recorded.

All AEs with moderate or greater intensity and/or possibly or probably related to the study drug(s) or study procedure must be followed by the investigator until it is resolved or until the medical condition of the subject is stable; all relevant follow-up information will be reported to the sponsor.

The outcome of an AE will be classified as recovered/resolved, recovered/resolved with sequelae, recovering/resolving, not recovered/not resolved, fatal or unknown.

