8.6.1 Adverse Events

Adverse events will be summarized by presenting, for each treatment group, the number and percentage of subjects having any AE, having an AE in an individual body system, and having each individual AE. Any other information collected (e.g., severity or relatedness to study medication) will be listed as appropriate.

Adverse events will be summarized by the Medical Dictionary for Regulatory Activities (MedDRA) system organ class and preferred term. The incidence of AEs (percent of subjects reporting the AE at least once) will be tabulated separately for each treatment group by severity and relationship to drug.

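### The AE severity scale has no criterion for symptom-free laboratory or blood-pressure abnormalities, so the by-arm severity table cannot show how large they were

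*Combined protocol and SAP*

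**What the plan says.** Section 7.4.1.3 of the protocol has three grades. The middle one, moderate, is worded "The signs and symptoms were sufficient to restrict, but did not prevent, usual daily activity for the subject". The lowest grade, mild, asks that the person noticed something and bore it without difficulty. The highest, severe, asks that normal activities became impossible. The closing sentence of the section, on maximum intensity, also speaks only of symptoms. No laboratory or vital-sign threshold is given there or elsewhere in the document.

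The AE definition is wider than the scale. Section 7.4.1.2 includes "any unfavorable and unintended sign (including an abnormal laboratory finding), symptom, or disease temporally associated with the use of the product", and 7.4.1.1 collects clinically relevant abnormalities that the investigator observes, laboratory measurements among them. Intensity must be recorded for each AE, and an AE whose intensity worsens is entered as a new AE.

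The grade is used in two further places. In 8.6.1, AE incidence "will be tabulated separately for each treatment group by severity and relationship to drug". In 7.4.1.1, "All AEs with moderate or greater intensity and/or possibly or probably related to the study drug(s) or study procedure must be followed" until resolved or stable.

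Section 2.5 lists the common reactions to oral sirolimus, including "hypertriglyceridemia, hypertension, hypercholesterolemia, creatinine increased".

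**The concern.** Many of the harms that the protocol cites for this drug appear first as a number, not as something a child feels. If the only severity scale asks what the subject noticed and could do, a slight and an extreme triglyceride, creatinine or platelet result can carry the same grade, or none. The severity table could then look alike for 0.4%, 0.2% and placebo although the values behind it differ. The same grade feeds one limb of the follow-up duty, and it decides whether a rising value counts as a worsened AE.

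**Working it through.** The document gives no figure to reproduce. The check is a reading of the passages against each other, plus one count.

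**1. Apply the scale to a symptom-free abnormal value recorded as an AE.**

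- Severe: not met, because daily activity is not prevented.
- Moderate: not met, because daily activity is not restricted.
- Mild: not strictly met, because the subject is not aware of anything. Awareness is an awkward test in any case for subjects as young as 2 years (5.2).

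So the two upper grades are closed at any value. In practice the entry will be mild by default, or it has no valid grade.

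**2. Consequence for worsening (7.4.1.1).** A silent value that climbs between visits does not change intensity under 7.4.1.3, so the new-AE rule is not triggered.

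**3. Consequence for follow-up.** The duty in 7.4.1.1 has two limbs joined by and/or. For a symptom-free AE the severity limb is never met, which leaves relatedness, with the five categories of 7.4.1.4:

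| Relatedness | Severity limb | Relatedness limb | Duty under the wording |
|---|---|---|---|
| Not Related | not met | not met | none |
| Probably Not Related | not met | not met | none |
| Possibly Related | not met | met | applies |
| Probably Related | not met | met | applies |
| Related | not met | category not named | unclear |

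Two categories are covered, two are not, and one is not named. Probably Not Related is defined so that a link to the product cannot be excluded.

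**4. What else shows the values by arm.**

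- Laboratory: 8.6 bases safety partly on counts of values outside predetermined ranges. Section 8.6.2 adds shift tables to the most extreme post-baseline value, summary statistics of raw values and changes, and flags. The predetermined, extended and notable limits are not stated in the document.
- Blood pressure: 8.6 and 8.6.2 provide listings and flags only. The AE table is the one by-arm display specified in which raised blood pressure could appear, and its severity column says nothing about a silent case.

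**5. Relevance to this drug.** The list in 2.5 has 15 reactions reported at more than 30%. Six are laboratory or blood-pressure findings: hypertriglyceridemia, hypertension, hypercholesterolemia, creatinine increased, anemia and thrombocytopenia. 6 / 15 = 40%. The tests in 7.4.4 and the vital signs in 7.4.6 already measure all six.

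**The case against.** Four stronger readings are tempting, and the documents support none of them.

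- *Every such AE is tabulated as mild.* The text does not say so. Mild requires awareness, so mild is a likely default and not a stated outcome.
- *Such AEs drop out of follow-up.* The relatedness limb catches those rated possibly or probably related at any severity, which is most suspected drug toxicity. Other routes do not depend on the grade either: serious important medical events (7.4.2, 13.2.2), AEs leading to discontinuation or withdrawal (5.4, 7.4.1.7), and repeat sampling in 7.4.4, which is permissive.
- *Extreme laboratory values are hidden from the safety analysis.* They are not. The out-of-range counts, shift tables and summary statistics can show a difference between arms.
- *40% of safety events would be misgraded.* The count comes from the oral label. Section 2.2 expects topical plasma levels near or below 0.1 ng/mL, 2.5 expects very low exposure, and anemia and hypertension are not always silent.

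It can also be argued that 7.4.1.3 speaks of signs as well as symptoms, and that 7.4.1.2 counts an abnormal laboratory finding as a sign. That brings the finding within the scale, but the grade still turns on tolerance and activity, not on the value.

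Finally, 8.1 and 8.6 defer detail to a SAP whose text is not in the document supplied, so further safety tables may be planned there. This stands for the tables. It does not help with the grade, which investigators must assign when they record the AE.

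**Conclusion.** The point holds in a limited form. The written scale cannot grade a symptom-free laboratory or blood-pressure AE above mild and may not grade it at all. For these events the severity column of the 8.6.1 table is therefore uninformative about size, and a rising silent value is never a worsened AE. For laboratory tests the loss is partly made good by the by-value analyses. For blood pressure it is not, since no by-arm summary of its values is specified. In follow-up, the gap is confined to AEs rated not or probably not related, with an unclear position for Related.

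The number of affected events cannot be estimated from the documents. With about 15 subjects per arm (45 / 3) and very low expected exposure it may be small. But safety is a stated objective (3.0), and 2.5 describes this as a first multiple-dose human trial and the earlier topical studies as small. Low exposure makes such events less frequent; it does not supply a grade. The point is worth correcting, but it does not touch the primary endpoint.

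The conclusion assumes that investigators apply 7.4.1.3 as written and that no value-based scale is supplied to sites in a separate document.

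**What to change.** 1. In 7.4.1.3, state that an AE which is a laboratory or blood-pressure abnormality is graded from the measured value on a named published scale, with limits suited to the subject's age and sex (2 to 21 years). Keep the activity scale for symptomatic events.
2. In 8.6.2, add a programmed by-arm table of the worst post-baseline value or grade in the double-blind period for blood pressure, triglycerides, cholesterol, creatinine, hemoglobin and platelets. Table 1-1 already schedules these at Weeks 4 and 12 and at early termination. Footnote that 7.4.4 states no fasting condition for triglycerides (only glucose has one, and it differs for China) and that China uses local laboratories, so sampling conditions and reference limits may differ between countries.
3. Reconcile the follow-up wording in 7.4.1.1 with the severity definitions in 7.4.1.3 and the five categories in 7.4.1.4. Which events are to be followed, and for how long, is for the sponsor to decide.

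The cost is a short protocol change and one derived table; no new visits or samples are needed. The sponsor must choose the scale and its reference limits and program them across two laboratory arrangements. Some events now called mild will be reported at a higher grade, and under the present wording of 7.4.1.1 those that reach moderate would then meet its severity limb.

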7.4.1.4 Relationship of an Adverse Event to Study Treatment

The investigator is to classify the relationship of an AE to the investigational product using good clinical judgment and the following definitions:

Not Related

The AE is clearly explained by another cause not related to the study product.

Probably Not Related	A potential relationship between study product and the AE could exist (i.e., the possibility cannot be excluded), but the AE is most likely explained by causes other than the study agent.
Possibly Related	The AE and administration of study product are temporally related, but the AE can be explained equally well by causes other than the study product.
Probably Related	The AE and use of study product are temporally related, and the AE is more likely explained by study product than by other causes.
Related	The AE and use of study product are related in time, and a direct association can be demonstrated.

7.4.1.5 Unexpected Adverse Events

See the Investigator's Brochure to determine expectedness of serious adverse events for expedited reporting. An AE is considered "unexpected" if it is not listed in the Package Insert of the marketed sirolimus oral products or in the Investigator's Brochure, or is not listed at the specificity or severity that has been observed; or, is not consistent with the risk information described in the general investigational plan or elsewhere in the current application, as amended.

7.4.1.6 Adverse Events of Special Interest

There are currently no known adverse events of special interest. The investigator should evaluate any reactions in the treatment area. If a subject has any reaction in the treatment area, the subject should return to the site for evaluation.

7.4.1.7 Adverse Events Causing Treatment Discontinuation

If a patient is withdrawn from the study as a consequence of an AE, this must be recorded and reason provided in the eCRF, and the patient must be followed until the resolution of the AE or as instructed by the Medical Monitor.

7.4.2 Serious Adverse Events

A serious adverse event (SAE) is any untoward medical occurrence that at any dose:

- is life-threatening
- results in death
- requires in-patient hospitalization or prolongation of existing hospitalization
- results in persistent or significant disability/incapacity
- is a congenital anomaly/birth defect

- is an important medical event.

The death of a subject enrolled in a study is per se not an event, but an outcome. Any event resulting in a fatal outcome must be fully documented and reported, regardless of the causality relationship to the investigational product.

The term life-threatening refers to an AE in which the subject was at immediate risk of death at the time of the event. It does not refer to an event, which may have caused death, if it was more severe.

Medical and scientific judgment should be exercised in deciding whether expedited reporting is appropriate in other situations, such as important medical events that may not be immediately life-threatening or result in death or hospitalization but may jeopardize the subject or may require intervention to prevent one of the other outcomes listed in the definition above. These should also usually be considered serious. Examples of important medical events include AEs, which suggest a significant hazard, contraindication or precaution, occurrence of malignancy, or development of drug dependency or drug abuse.

Any SAE, whether or not deemed drug-related or expected, must be reported immediately to the sponsor or designee via email as soon as it becomes known to the investigator and not later than within 24 hours of his/her knowledge of the occurrence of an SAE. The investigator will document such events in the best possible detail on the SAE Report Form to be transmitted by email. SAEs will be collected from the time the subject signs informed consent/assent until 30 days after the last investigational product administration.

A pre-scheduled elective procedure is not to be considered an SAE, even if the subject is hospitalized, provided the condition requiring the pre-scheduled elective procedure was present before and did not worsen or progress between the subject's consent to participate in the study and the time of the procedure. In addition, the pre-scheduled elective procedure must be the sole reason for admission and intervention. An adverse event occurring during the pre-scheduled elective procedure should be recorded as an AE or SAE.

A suspected unexpected serious adverse reaction (SUSAR) is an SAE that is both unexpected (not consistent with the current Investigator's Brochure/product information) and for which there is evidence to suggest a causal relationship between the drug and the AE. As a minimum requirement, the Investigator must report all SUSARs to their IRB. All investigators participating in the trial will also be notified appropriately of SUSARs. The sponsor will report SUSARs and other events requiring expedited reporting to regulatory authorities as required.

Investigator instructions for reporting SAEs are provided in [Section 13.2](#).

7.4.3 Dermatologic Stopping and Follow-up Criteria

Dermatologic stopping criteria are defined below:

If a subject has worsening angiofibromas where the investigator feels the worsening has a causal relationship to the study drug, the study drug should be stopped. If the investigator would like to restart the drug within 7 days as a re-challenge, they can do this in consultation with the Medical Monitor. A second re-challenge will not be allowed and the subject should be discontinued.

If the investigator feels that the angiofibromas are worsening (such as 2 grades higher on the IGA) that is abnormal in disease progression and the investigator feels it is not in the subject's best medical interest to continue in the study, they can schedule an early termination visit and discontinue the subject.

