7.2.6 Early Termination (Blinded and Open-Label)

If a subject withdraws from the study prior to the End of Study visit, the subject is to return to the site. The early termination procedures should be performed, as specified below:

- Collect all study materials from the subject (or parent/guardian), including used and unused study medication, subject dosing diary, etc.
- Weigh the used tubes of study medication collected from the subject.
- Review any concomitant medication used since the previous study visit.
- Perform a physical examination, including height and weight.
- Measure vital signs (systolic and diastolic blood pressure, heart rate, and respiratory rate) with subject in a seated position.
- Obtain blood samples and optional urine samples for a laboratory profile including hematology, clinical chemistry, and urinalysis.
- Perform a UPT for females of childbearing potential. Remind sexually-active female subjects of childbearing potential to use approved method(s) of contraception. Remind sexually active male subjects that they (or their female partners) should use appropriate contraception. (In the unlikely event that a urine pregnancy test cannot be obtained, a serum pregnancy test can be run from the serum sample collected.) (For China, different pregnancy test procedure would be followed).
- Perform the following efficacy assessments:
 - Investigator's Global Assessment (IGA);
 - Facial Angiofibroma Severity Index (FASI) (assessment of erythema, size, and extension);
 - Modified Nobel Scoring System (assessment of target lesions and non-target lesions response);

- Categorical lesion count using the following categories: (0) no lesion; (1) <25 lesions; (2) 25-50 lesions; (3) 51-75 lesions; (4) >75 lesions;
- Assessment of lesion elevation.
- Have the subject (or parent/guardian for subjects under the developmental age of 7 years) complete the subject self-assessment survey.
- Take a photograph of the angiofibroma according to the Standardized Operation Procedure (Appendix 2).
- Record any AEs.
- Inform Subjects that they may be approached to participate in future trials with this product.
- Dismiss the subject from the study.

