8.0 STATISTICAL METHODS AND DETERMINATION OF SAMPLE SIZE STATISTICAL AND ANALYTICAL PLANS

8.1 General Considerations for Data Analysis

The methodology presented below represents a brief overview of the statistical methods that will be fully detailed in the statistical analysis plan (SAP). The SAP will be finalized before the database is locked and unblinded. Any changes to the methods described in the final SAP will be described and justified in the clinical study report. It is planned that the data from all centers that participate in this protocol will be combined so that an adequate number of subjects will be available for analysis. All statistical analyses will be performed using SAS statistical software (Version 9.2 above).

Statistical significance will be tested at the 2-sided 5% level. No adjustments for multiplicity are planned.

All efficacy and safety analyses will be performed on observed data with no imputation unless otherwise specified. For the analyses of treatment response, subjects having a missing responder status will be analyzed as non-responders.

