8.3 Analysis Populations

The primary statistical analyses will be performed on the Intent-to-Treat (ITT) population (efficacy), Per-Protocol population (efficacy) and Safety population (safety). The analysis populations are defined as:

- Intent-to-Treatment (ITT) population will include all randomized subjects. This will be the population for efficacy analysis.
- The Per-Protocol (PP) population will include all ITT subjects with no major protocol deviation and with >80% study drug compliance rate, where the drug compliance will only apply to active treatment groups. Efficacy analyses will be repeated on this population as a sensitivity analysis.
- Safety population will include all subjects who were randomized and dispensed the study medication at Randomization / Day 1, excluding subjects who return all of the study medication unused. This will be the population for safety analysis.

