8.5.2 Secondary Efficacy Endpoints

Secondary efficacy endpoints will be the following:

- The proportion of subjects with an investigator assessed IGA score of clear or almost clear with at least a 2-grade improvement on the Week 12 IGA of the facial skin lesions;
- The proportion of subjects with at least 30% improvement at Week 12 as compared to Baseline in the Facial Angiofibromas Severity Index (FASI) score, which is based on lesion erythema, size, and extension (Salido et.al. 2012);²⁰
- The time to reach at least 30% improvement from Baseline in the FASI score for angiofibroma severity;
- The proportion of subjects with at least 2-grade improvement at Week 12 as compared to Baseline in categorical lesion counts (scored as follows: No lesion = 0; <25 lesions = 1; 25-50 lesions = 2; 51-75 lesions = 3, >75 lesions = 4);
- The proportion of subjects with at least 2-grade improvement at Week 12 as compared to Baseline in lesion elevation score;
- The proportion of subjects with at least 2-grade improvement at Week 12 as compared to Baseline in the subject self-assessment survey;
- Overall Response of angiofibroma assessed by the investigator at Week 12 as compared to baseline based on Modified Nobel Scoring System;
- Overall Response of angiofibroma assessed by the IRC at Week 12 as compared to baseline based on Modified Nobel Scoring System;

- The proportion of subjects with at least Moderate Improvement (a score of 2) on Modified Nobel Scoring System assessed by the investigator at Week 12;
- The proportion of subjects with at least Moderate Improvement (a score of 2) on Modified Nobel Scoring System assessed by the IRC at Week 12;
- The proportion of subjects with at least a 2-grade improvement on Week 12 Investigator Global Assessment (IGA) of the facial skin lesions assessed by the IRC.

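### As the protocol is written, subjects who leave before Week 12, including those dismissed for worsening, have no value in the two ordinal Modified Nobel Overall Response tests

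*Combined protocol and SAP*

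**What the plan says.** **Who can leave.** Section 7.4.3 has two paragraphs on worsening.
- The first covers worsening that the investigator attributes to study drug. Drug is stopped and one re-challenge is possible, after which "A second re-challenge will not be allowed and the subject should be discontinued". It does not say whether that means off drug or out of the study.
- The second covers abnormal worsening, with a two-grade rise in IGA as an example, where staying in the study is judged not to be in the subject's interest. Investigators then have an option: "they can schedule an early termination visit and discontinue the subject".

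Sections 5.4 and 6.9 add other routes out, such as the subject's own request, a serious adverse event and non-compliance.

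**What is collected on leaving.** The Early Termination visit (7.2.6) includes the Modified Nobel assessment and photographs ("Take a photograph of the angiofibroma according to the Standardized Operation Procedure"). The last step is "Dismiss the subject from the study".

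**How it is analysed.** Section 8.3 says that the ITT "population will include all randomized subjects". Section 8.1 says: "All efficacy and safety analyses will be performed on observed data with no imputation unless otherwise specified". The only exception in the supplied text is that "subjects having a missing responder status will be analyzed as non-responders". Section 8.5.2 lists "Overall Response of angiofibroma assessed by the investigator at Week 12" as a secondary endpoint, with a matching one for the IRC, and compares the Modified Nobel score by Wilcoxon rank sum test.

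**The concern.** The Overall Response scale (Table 7-9) has a bottom level, Worsened, for scores of -1 or less. The subjects most likely to fill it are those whom 7.4.3 can remove. Once dismissed they have no Week 12 score, and the observed-data rule gives them none. The two Wilcoxon comparisons would then be made on a subset selected partly by outcome, although the stated population is everyone randomized.

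Losing such subjects from an active arm flatters that arm; losing them from placebo works against the drug. With 45 subjects allocated 1:1:1, one or two such losses are a visible fraction of an arm. The needed information is already collected at the Early Termination visit, but nothing says that it may stand in for Week 12.

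**Working it through.** **Step 1: does the exception in 8.1 reach this endpoint?** It assigns non-response when responder status is missing. On Table 7-9, scores of -1, 0 and 1 all fall below Moderate improvement, so non-responder is not a score and cannot be ranked. The exception covers the proportions with at least Moderate improvement, but not the ordinal Overall Response. No section of the supplied text maps an Early Termination score to Week 12.

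**Step 2: can a few losses matter?** The plan states no power, effect size or dropout rate to reproduce (8.2), so what follows is illustration. From the documents: 45/3 = 15 per arm, two-sided 5% level, Wilcoxon test. All scores are assumed.

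Formulas, with n_A active and n_P placebo subjects, N = n_A + n_P, W the active rank sum and t the size of each tie group:
- U = W − n_A(n_A+1)/2
- mean μ = n_A·n_P/2
- variance = (n_A·n_P/12)·[(N+1) − Σ(t³−t)/(N(N−1))]
- z = (|U−μ| − 0.5)/SD

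*Example A, two active subjects stopped.* Placebo: nine 0, four 1, two 2. Active stayers: three 0, four 1, four 2, two 3.
- Omitted (13 v 15): W = 234.5, U = 234.5 − 91 = 143.5, μ = 97.5. Tie groups 12, 8, 6, 2 give Σ = 2436. Variance = 16.25 × (29 − 2436/756) = 418.9, SD = 20.47, z = 45.5/20.47 = 2.22, **p = 0.026**.
- Scored -1 (15 v 15): U = 143.5, μ = 112.5, SD = 22.99, z = 30.5/22.99 = 1.33, **p = 0.185**.
- Scored 0, as if recovered to unchanged: U = 152.5, SD = 22.51, z = 39.5/22.51 = 1.75, **p = 0.079**.

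*Example B, two placebo subjects stopped.* Active: four 0, five 1, four 2, two 3. Placebo stayers: eight 0, three 1, two 2.
- Omitted (15 v 13): U = 137.5, μ = 97.5, SD = 20.47, z = 39.5/20.47 = 1.93, **p = 0.054**.
- Scored -1: U = 167.5, μ = 112.5, SD = 22.99, z = 54.5/22.99 = 2.37, **p = 0.018**.
- Scored 0: U = 163.5, SD = 22.51, z = 50.5/22.51 = 2.24, **p = 0.025**.

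**Step 3: averaged over possible data.** Assume stayers score 0/1/2/3 with probabilities .55/.30/.12/.03 on placebo and .25/.33/.27/.15 on active. Enumerating every table of score counts with the same test gives the chance of p < 0.05 favouring active:

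| Stops (active, placebo) | Omitted | Scored -1 | Scored 0 |
|---|---|---|---|
| 0, 0 | 49% | 49% | 49% |
| 1, 0 | 48% | 28% | 37% |
| 2, 0 | 46% | 11% | 26% |
| 3, 0 | 44% | 2% | 16% |
| 0, 1 | 47% | 58% | 54% |
| 0, 2 | 46% | 67% | 60% |
| 0, 3 | 44% | 76% | 66% |
| 2, 2 | 43% | 22% | 36% |
| 1, 2 | 44% | 45% | 48% |

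**Step 4: false positives.** If stayers have the same score distribution in both arms (the placebo probabilities above) and two active subjects are omitted, the test rejects 2.3% + 2.3% = 4.6% of the time. A separate simulation (6000 replicates) assumed that 20% of subjects worsen in each arm and that treatment has no effect. Dismissing half of the worsened subjects in both arms left the chance of a result favouring active near 2.5%. Dismissing every worsened active subject and no placebo subject raised it from about 2.1% to 14.3%, but that pattern is extreme.

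**The case against.** **The SAP may already cover it.** Section 8.1 calls itself an overview and defers detail to a SAP to be finalized before lock and unblinding. No separate SAP text is in the supplied document, so a reader should not infer that the final analysis will certainly omit these subjects. This stands. But 8.1 is not merely silent: it states a default, and that default leaves them out unless something else is specified.

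**The important readouts are safe.** A reader might infer that the primary result is at risk. It is not: non-responder handling covers the primary IGA endpoint and the other yes/no endpoints, including at least Moderate improvement on this same instrument by investigator and by IRC. What remains is two ordinal tests among eleven secondary endpoints, in a trial that 8.2 calls exploratory. This stands and limits the weight of the point.

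**Few subjects may be affected.** Entry IGA is 3 to 5 and the scale stops at 5, so a two-grade rise is possible only from grade 3, although that figure is only an example. Between Baseline and Week 12 the only scheduled clinic visit is Week 4; Week 8 is by telephone. The second paragraph of 7.4.3 is discretionary, and the first begins by stopping drug only. An Early Termination visit falling within Day 84 ± 7 might be taken as Week 12, though no rule says so. All this is fair; the number of losses is unknown and may be zero.

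**The illustrations are built on assumptions.** No stayer is allowed to be worsened, and the largest effects need all stops in one arm, while investigators are blinded. Also true. A reader might infer a bias towards sirolimus or a general inflation of false positives. The documents support neither: 2.1 reports improvement in all published cases, so stops on placebo are at least as plausible, and Step 4 shows no inflation in the balanced case.

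**Conclusion.** The concern holds in limited form. On the supplied text, a subject without a Week 12 Modified Nobel score, whatever the reason, contributes nothing to the two Overall Response Wilcoxon tests, and losses under 7.4.3 are related to the outcome being tested. Direction and size cannot be stated, because the documents give no stop rate and no score distribution. With about 15 per arm, two such losses can carry an illustrative p-value across 0.05 either way, even if those subjects are scored as recovered to unchanged: 0.026 against 0.079 for active stops, 0.054 against 0.025 for placebo stops. With no losses there is no effect. The conclusion rests on 8.1 being applied as written and on no further rule in a SAP that was not supplied. Minor to moderate: a cheap improvement to the interpretation of two secondary tests.

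**What to change.** **(a) Section 8.1 and the SAP, before the Week 12 lock and unblinding described in 8.4.** Suggested rule:

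> If the Week 12 Modified Nobel Overall Response is missing for any reason, the Early Termination score is used; for the IRC, its reading of the Early Termination photographs is used. If there is none, the subject is placed in the lowest category (Worsened, -1 or less). The observed-only analysis is reported as sensitivity.

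Applying the rule to every reason for missingness keeps it independent of how a withdrawal is labelled, and the lowest category matches the spirit of the non-responder rule. Because target and non-target scores can add to -2, rank the Table 7-9 categories, so that -1 and -2 tie.

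**(b) Section 7.4.3.** In the first paragraph, say that study drug is stopped permanently and that the subject is asked to attend the scheduled visits through Week 12. In the second, offer the same unless the investigator judges it against the subject's medical interest or consent is withdrawn. An actual Week 12 score, when obtained, takes precedence over the Early Termination score.

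**Cost.** One rule, short wording in 7.4.3, and a few off-drug visits that are already in the schedule; no new assessments. The drawback is that an Early Termination score can predate Week 12, by about eight weeks for a stop at Week 4, and so miss recovery. The scored-0 column in the working shows how much that could matter, and follow-up under (b) reduces it.
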